- D. All patients may receive 4-6 months (+/- 2 months) of ADT at the discretion of the treating physician, if the patient agrees. Patients with Gleason score ≥8 must be offered long term androgen deprivation therapy (ADT) and refuse such treatment because only 4-6 months (+/- 2 months) (short term ADT) is permitted (not required) on this protocol. The ADT is recommended to begin after fiducial marker placement; however, is permitted to have been started up two months prior to the signing of consent.
- E. PSA ≤30 ng/mL within 3 months of enrollment.
- F. No previous pelvic radiotherapy.
- G. No previous history of radical/total prostatectomy (suprapubic prostatectomy is acceptable).
- H. No concurrent, active malignancy, other than non-metastatic skin cancer or early stage chronic lymphocytic leukemia (well-differentiated small cell lymphocytic lymphoma). If a prior malignancy is in remission for ≥ 5 years then the patient is eligible.
- I. Identifiable multiparametric MRI-defined tumor lesion or lesions, that total in volume <33% of the prostate.
- J. Ability to understand and the willingness to sign a written informed consent document.
- K. Zubrod performance status <2.

- L. Patients must agree to fill out the psychosocial questionnaires.
- M. Bone scan negative if PSA >15 ng/mL or Gleason \geq 8 disease. A questionable bone scan is acceptable if plain x-rays and/or MRI are negative for metastasis.
- N. Serum testosterone is within 40% of normal assay limits (e.g., $x=0.4$ *lower assay limit and $x=0.4$ *upper assay limit + upper assay limit), taken within 4 months of enrollment. Patients who have been started on ADT prior to signing consent are not required to have a serum testosterone at this level prior to signing consent; but, a serum testosterone prior to fiducial marker placement is recommended.
- O. Serum liver function tests (LFTs) are taken within 3 months of enrollment.
- P. Complete blood counts are taken within 3 months of enrollment.
- Q. Age \geq 35 and \leq 85 years.

2. After Enrollment and Prior to Treatment

- A. Transrectal research prostate biopsies and gold seed fiducial marker placement:
 - a. The pre-RT prostate biopsy is optional for the patient, while the fiducial marker placement is not. For the prostate biopsies, up to a maximum of 14 cores will be taken prior to fiducial marker placement. The number of biopsy cores taken would be up to the discretion of the urologist in conjunction with the team, and does not have to be defined prior to biopsy if the patient agrees to undergo the procedure.
 - b. Ultrasound-guidance is standard for prostate biopsies. The Eigen Artemis® system may be used to fine tune the biopsy locations within the prostate using software to fuse the multiparametric MRI to the ultrasound in real time as the ultrasound is acquiring the images. In addition, these biopsies may be obtained on an MRI directly using established techniques.
 - c. 3-4 gold seeds placed in prostate (4 preferred)
- B. MRI-simulation: Limited study without contrast at least 1 week after gold fiducial placement.
- C. CT-simulation and planning.

3. Treatment Technique

- A. LEAD RT: 12-14 Gy dose pipes on day 1.

The LEAD dose distribution may be planned and delivered by the Cyberknife, an image-guided robotic SBRT system, or on a standard LINAC,. The LEAD RT dose plan will involve the placement of 1 to 3 dose pipes of 7-12 mm diameter the length of the multiparametric MRI GTV volume; but, may extend up to 6 mm above and 6 mm below the GTV. The GTV will include the multiparametric MRI-defined suspicious lesions defined by either early phase contrast enhancing lesion on dynamic contrast enhanced (DCE)-MRI or water restriction on the Apparent Diffusion Coefficient (ADC) maps, considered with the abnormality on T2-weighted imaging. For anterior lesions in the transition zone an abnormality based on only DCE-MRI is not enough and must be accompanied by, restricted water motion on diffusion weighted imaging (DWI) via an ADC point value of <1000 and/or increased choline + creatinine relative to citrate (\geq 0.9 ratio) on MR spectroscopy (MRS). The LEAD RT region(s) will be centered in the GTV region(s), but may extend out of the GTV to avoid being too close to the vital structures (rectum, urethra, bladder or penile bulb. The LEAD regions should be positioned \geq 2 mm from the vital structures to avoid excessive dose to these structures. Up to three dose pipes spaced by approximately 1.5 – 2.0 cm may be used, with no more than two per side of the prostate. The LEAD RT dose pipes will be covered by 12-14 Gy with a maximum of 20 Gy. The

maximum dose for each dose pipe shall be <20 Gy. A variation will be maximum doses ≥ 20 Gy to 23 Gy, with a protocol violation above this limit. The Vprescription (12-14 Gy) is expected to be <20% and >10% of the tumor, but this is not a constraint. The V(3 Gy) for the rectum, bladder, and penile bulb will be <8% (4.0 Gy Dmax). Protocol variations will be a V(3 Gy) of 8-10% with a Dmax of 4.5 Gy. A protocol violation will be anything above these limits. For the urethra, the V(3 Gy) will be <10%. A protocol primary variation will be a V(3 Gy) of 10-20% with a Dmax of 6.0 Gy. A secondary protocol variation will be for any dose above the limits; there will not be any protocol deviations for the urethral dose. The urethra is more resistant to higher radiation doses; hence, the more relaxed constraints.

B. IMRT: Start of 76 Gy in 2 Gy fractions on day 2 (within 32 hr of LEAD RT).

There shall be no gap of more than 30 hours between the first three 2 Gy fractions; the LEAD RT treatment will therefore be done on a Monday, Tuesday, or Wednesday, unless special arrangements are made to treat on the weekend. In-tempo image-guided technique will be used to deliver both the LEAD and the fractionation treatments to minimize the dosimetric error from intra-fractional prostate movement. The primary Clinical Target Volume (CTV1) will include the prostate (with GTV) and the proximal seminal vesicles (usually about 10 mm and/or $\leq 50\%$). The CTV1 may include an extra 1-2 mm beyond the GTV in regions of known bulky disease and/or extracapsular extension as determined by the diagnostic biopsy information and/or MRI. The Planning Target Volume (PTV1) will be 3-5 mm around the CTV1 in all dimensions. For tumors at the base, a margin of 5 mm on the proximal seminal vesicles is recommended.

The pelvic lymph nodes may be treated in high risk patients (CTV2) to 56 Gy in the planned 38 fractions. There is no expansion for the PTV2.

IMRT plans will be evaluated by dose-volume histogram analysis. Less than or equal to 17% and 35% of the rectum should receive ≥ 65 Gy and ≥ 40 Gy, respectively, in calculated 2 Gy equivalent doses.¹ Less than or equal to 25% and 50% of the bladder should receive ≥ 65 Gy and ≥ 40 Gy, respectively, in calculated 2.0 Gy equivalent doses. At least 95% of the PTVs should receive the prescription dose (a minor variation will be <95% to $\geq 90\%$ of the prescription dose). Assuming an α/β ratio of 3.0, the biologically equivalent dose in 2.0 Gy fractions to the LEAD RT region would be 149 Gy.

Eligibility Checklist

- _____ 1. Biopsy confirmed adenocarcinoma of the prostate.
- _____ 2. All must be within limits:
- _____ Palpable Stage T1a-T3a (AJCC 2002 staging system) (Y/N).
- _____ T1a is permitted if peripheral zone biopsies are positive (Y/N).
- _____ MRI-defined \leq T3a disease (Y/N).
- _____ PSA \leq 30 ng/ml within 3 months of enrollment. If PSA was above 20 and dropped to \leq 20 with antibiotics, this is acceptable for enrollment. (_____) **Fill In Value**
- _____ If PSA is >15 ng/ml or Gleason 8 disease, has a bone scan been obtained \leq 4 months before enrollment that is negative for metastasis (Y/N vs. **N/A**)? A questionable bone scan is acceptable if plain x-rays and/or MRI are negative for metastasis.
- _____ Gleason score 6-10. (_____) **Fill In Value**
- _____ If Gleason score \geq 8: Refused long term androgen deprivation therapy (ADT) (Y/N)?
- _____ If Gleason score \geq 8: Is there <40% Gleason 8-10 tumor, over the total tissue including other tumor and normal tissue (Gleason 8 tumor length/other biopsy tissue length]*100 = <40%) (Y/N)?
- _____ Is ADT for 4-6 months (+/- 2 months) planned (Y/N)?
- _____ If yes, for how many months? (4, 5 or 6 mo)
- _____ Multiparametric MRI abnormality of <33% of the prostate volume.
- _____ If no contrast for multiparametric MRI, was ADC map point dose in T2W abnormality <1000 (Y/N)?
- _____ 3. Is the patient currently on ADT? (Y/N)
- _____ If Yes, was the ADT started \leq 2 months prior to signing the consent (Y/N)
- _____ 4. Zubrod performance status of 0-1.(Y/N) (Karnovsky or ECOG performance status may be used to estimate Zubrod) Performance status is (_____) **Fill In Value**.

- _____ 5. Was the serum testosterone level, drawn as a baseline study in patients not started on androgen deprivation therapy prior to signing consent (Y/N)? Note that serum testosterone is only required for study entry for those not previously started on ADT and should be obtained in applicable patients ≤ 4 months before signing consent. (_____) **Fill In Value.** Serum testosterone is within 40% of normal assay limits for those not started on ADT (a serum testosterone level is still recommended prior to fiducial pmarker placement in those started on ADT prior to signing consent).
- _____ 6. No prior pelvic radiotherapy (Y/N).
- _____ 7. No prior or planned radical prostatectomy (Y/N).
- _____ 8. No concurrent, active malignancy, other than non-metastatic skin cancer or early stage chronic lymphocytic leukemia (well-differentiated small cell lymphocytic lymphoma) (Y/N).
- _____ 9. Is patient willing to fill out psychosocial questionnaires (Y/N)?
- _____ 10. Ability to understand and willing to sign a written informed consent document. (Y/N)
- _____ 11. Serum liver function tests (LFTs) are taken within 3 months of enrollment. (Y/N)
- _____ 12. Complete blood counts are taken within 3 months of enrollment. (Y/N)
- _____ 13. Age ≥ 35 and ≤ 85 years. (Y/N)

Signature

Date

HYPOTHESIS

1. Delivery of single fraction Lattice Extreme Ablative Dose (LEAD) RT to the dominant tumor lesion(s) in the prostate as identified by multiparametric functional Magnetic Resonance Imaging is safe and feasible.
2. Biomarker expression levels differ in the functional MRI identified suspicious and unsuspected tumor regions. We hypothesize that a significant source of variation in biomarker levels is due to tumor heterogeneity and that it is molecular abnormalities in the dominant tumor areas that are angiogenic and determine outcome.

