real time target tracking is preferred, but not required in the LEAD boost portion of the treatment. The Cyberknife may be used for both the LEAD RT single fraction treatment as well as the whole prostate standard fractionation treatments that follow for 38 fractions. The 38 standard dose and fractionation treatments are to the prostate and proximal seminal vesicles, and may also involve the simultaneous treatment of the distal SVs and pelvic lymph nodes in high risk patients, as desired by the treating physician. In summary, the LEAD RT and following 38 standard dose per fraction treatments may be done on the Cyberknife or a standard LINAC with image guidance for alignment prior to treatment delivery (real-time tracking is not required).

LEAD Timing: The LEAD treatment will be delivered and within 32 hr, the conventional fractionation treatment will follow. There shall be no gap between the first three daily 2 Gy fractions each delivered within 30 hr of each other; the LEAD RT treatment will therefore be done on a Monday, Tuesday, or Wednesday unless special arrangements are made to treat on the first Saturday.

LEAD Constraints: One to three pipes will be used to treat the larger lesions, with up to two on one side of the prostate; they will be spaced by 1.5 – 2.0 cm, if possible. The LEAD RT dose pipes will be covered by 12-14 Gy with a maximum of 20 Gy. The maximum dose for each dose pipe shall be <20 Gy. A variation will be maximum doses ≥ 20 Gy to 23 Gy, with a protocol violation above this limit. The Vprescription (12-14 Gy) is expected to be <20% and >10% of the tumor, but this is not a constraint. The V(3 Gy) for the rectum and bladder will be <8% (4.0 Gy Dmax). Protocol variations will be a V(3 Gy) of 8-10% with a Dmax of 4.5 Gy. A protocol violation will be anything above these limits. For the urethra, the V(3 Gy) will be <10%. A protocol primary variation will be a V(3 Gy) of 10-20% with a Dmax of 6.0 Gy. A secondary protocol variation will be for any dose above the limits; there will not be any protocol deviations for the urethral dose. The urethra is more resistant to higher radiation doses; hence, the more relaxed constraints.

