4.15 Duration of Therapy

- Within 4 weeks of enrollment, patients will be biopsied (patient may refuse) and fiducial markers placed.
- LHRH agonist androgen deprivation therapy: LHRH agonist therapy may start up to two months prior to signing consent form or any time after signing consent form, up to two weeks after fiducial marker placement (preferred) in men with intermediate or high (optional) risk prostate cancer. All patients may receive 4-6 months (+/- 2 months) LHRH agonist therapy.
- Anti-androgen treatment should begin 1-14 days prior to LHRH agonist injections. Anti-androgen will be continued four 4 months.
- .
- Standard fraction RT: Day 2 of radiotherapy will start within 32 hr of LEAD RT and will consist of 38 fractions at 2.0 Gy over 7.5 weeks
- Treatment will be stopped for grade 4 acute toxicity (according to the current version of Common Terminology Criteria for Adverse Events (CTCAE version 4), but may be resumed per protocol if the treatment break is less than 10 working days. Since we have never observed grade 4 toxicity acutely using IMRT (conformal CyberKnife treatment is an IMRT-like treatment),

such an event is unlikely. If grade 4 toxicity resolves beyond the 10 days the treating physician will decide whether to give additional RT.

- Treatment will be stopped if metastasis is detected by radiographic or pathologic evidence and the patient will be removed from the study, but not from intent-to-treat analysis. A work-up for metastasis during treatment will only be carried out if the treating physician deems necessary.
- Multiparametric MRI exams of the prostate/pelvis will be carried out after RT at 3 months, 9 months, and within 2 months of the post-treatment prostate biopsies.
- Prostate biopsies will be taken at 2-2.5 years post completion of all therapy.

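### The Monday-to-Wednesday list of LEAD days does not follow from the 30-hour limit: a Wednesday start breaks the limit unless Saturday is treated

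*Combined protocol and SAP*

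**What the plan says.** Schema item 3.B starts the conventional course the day after LEAD: "Start of 76 Gy in 2 Gy fractions on day 2 (within 32 hr of LEAD RT". It then sets a spacing limit, "There shall be no gap of more than 30 hours between the first three 2 Gy fractions", and draws a scheduling rule from it: "the LEAD RT treatment will therefore be done on a Monday, Tuesday, or Wednesday, unless special arrangements are made to treat on the weekend".

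Section 4.8 (LEAD Timing) repeats both parts. "The LEAD treatment will be delivered and within 32 hr, the conventional fractionation treatment will follow", and then "There shall be no gap between the first three daily 2 Gy fractions each delivered within 30 hr of each other". It gives the same three days, but its exception is narrower: "unless special arrangements are made to treat on the first Saturday".

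Section 4.15 agrees on the start ("Day 2 of radiotherapy will start within 32 hr of LEAD RT") and says that the course "will consist of 38 fractions at 2.0 Gy over 7.5 weeks". Section 6.1 also places the first 2 Gy fraction on the day after LEAD, and Section 1.2 gives one 2 Gy fraction per day. Section 5.2 lists the three LEAD days again, with no weekend exception.

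**The concern.** The hour limit and the day list stand in the same sentence, and the second is presented as a consequence of the first. Both are operative rules for delivering the experimental regimen. If a listed day does not satisfy the limit, staff who book LEAD from the list on a normal weekday calendar will exceed the protocol's own spacing rule within the first three conventional fractions. Anyone checking treatment records afterwards could not say whether such a patient was treated per protocol. Section 5.2 adds to the risk, because it shows the day list without the limit or the weekend condition.

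**Working it through.** **Inputs**
- LEAD to fraction 1: the next day, at most 32 h (Schema 3.B; Sections 4.8, 4.15, 6.1).
- Fraction 1 to 2, and fraction 2 to 3: at most 30 h each (Schema 3.B; Section 4.8). I apply the limit to consecutive fractions.
- One 2 Gy fraction per day (Sections 1.2 and 4.8).
- The plan's own result: Monday, Tuesday and Wednesday are acceptable without special arrangements.

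**Method.** For each LEAD day, place one fraction on each available treatment day after LEAD. The gap is 24 h × the number of calendar days between treatments. Compare the three gaps with 32 / 30 / 30 h.

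| LEAD | Weekdays only | Saturday added | Saturday and Sunday added |
|---|---|---|---|
| Mon | Tue, Wed, Thu: 24/24/24, meets | unchanged | unchanged |
| Tue | Wed, Thu, Fri: 24/24/24, meets | unchanged | unchanged |
| Wed | Thu, Fri, Mon: 24/24/**72**, fails | Thu, Fri, Sat: 24/24/24, meets | unchanged |
| Thu | Fri, Mon, Tue: 24/**72**/24, fails | Fri, Sat, Mon: 24/24/**48**, fails | Fri, Sat, Sun: 24/24/24, meets |
| Fri | Mon, Tue, Wed: **72**/24/24, fails | Sat, Mon, Tue: 24/**48**/24, fails | Sat, Sun, Mon: 24/24/24, meets |
| Days that comply | 2 of 5 | 3 of 5 | 5 of 5 |

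The plan's list is therefore not reproduced: on weekdays the rule as written gives Monday and Tuesday only.

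**Can clock time rescue Wednesday?** No. From the end of Friday to the start of Monday is 2 × 24 = 48 h, already above 30 h. In an assumed 07:00 to 19:00 treatment day, the shortest gap is 72 − 12 = 60 h.

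**Which rule would give the plan's list?** Suppose that only LEAD to fraction 1 (32 h) and fraction 1 to 2 (30 h) are limited, so that LEAD counts as one of three treatments. The first two gaps in each row then decide:
- weekdays only: Monday, Tuesday and Wednesday comply (3 of 5);
- Saturday added: Thursday also complies (4 of 5);
- both weekend days added: Friday also complies (5 of 5).

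The weekday result is exactly the plan's list.

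**The two exceptions differ.** Under the rule as written, the Schema's weekend wording can admit Thursday and Friday if both days are treated. Section 4.8 mentions only Saturday, which admits neither.

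**The case against.** The strongest reply is that the day list is right and the limit is misworded. If the limit was meant for LEAD plus two 2 Gy fractions, weekdays give exactly the three listed days, and a Saturday session adds Thursday, so the exception in Section 4.8 does real work. Under the rule as written, a Saturday session opens no day outside the list. This is good evidence of a possible intent, but not proof: Schema 3.B and Section 4.8 both name the first three 2 Gy fractions. Either way, the list and the limit disagree.

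A second reply is that the limit binds every start day, so a Wednesday start already requires a Saturday fraction, and Saturday treatment is allowed. It is true that both rules can be met together. But the sentence makes weekend treatment the exception to the list, which implies that listed days need no special arrangement, and Wednesday does.

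Nor does the stated course length show that Saturdays are excluded. Five fractions a week gives 38/5 = 7.6 weeks and six gives 38/6 = 6.3, so routine Saturday treatment is unlikely. One first Saturday is a different matter. After a Wednesday LEAD, three fractions from Thursday to Saturday and then seven five-day weeks make 3 + 35 = 38 fractions over 51 days, or 7.3 weeks. Weekdays only takes 54 days, or 7.7 weeks. The stated 7.5 weeks does not separate these. That weekend treatment is exceptional rests on the plan's calling it a special arrangement.

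Finally, no analysis depends on this gap. Feasibility concerns whether LEAD was delivered (Sections 9.1 and 14.2), and the stopping rules use acute grade 3 or higher GI/GU toxicity and LEAD ineligibility (Section 14.4). The plan defines variations and violations for dose but none for timing. All of this stands and limits the severity.

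**Conclusion.** The point holds, as a minor error of wording. On a weekday calendar, one of the three listed days, Wednesday, gives a gap of about 72 h between the second and third 2 Gy fractions (48 h at the very least) against a limit of 30 h. With a Saturday fraction the gap is 24 h.

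This assumes one fraction per day, the first on the day after LEAD, and a limit that means what it says about the first three 2 Gy fractions. The documents do not show whether the limit or the list carries the intended rule. They give no distribution of start days, so the number of patients affected is unknown; it could be anything from none to all 25. They show no clinical consequence of the longer gap.

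**What to change.** The sponsor should decide which rule is meant and put the same wording in Schema 3.B, Section 4.8 and Section 5.2.

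- **If the limit stands as written:** LEAD on Monday or Tuesday; on Wednesday only if the third 2 Gy fraction is given on the first Saturday; on Thursday or Friday only if both weekend days are treated.
- **If LEAD plus the first two 2 Gy fractions was meant:** keep Monday to Wednesday, and reword the limit so that the first 2 Gy fraction is within 32 h of LEAD and the second is within 30 h of the first. The weekend exception should then say that Thursday needs Saturday, and that Friday needs both weekend days.

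The cost is one sentence in three places. Under the first option, each Wednesday start also needs a Saturday session; under the second there is no operational cost.

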1.0 BACKGROUND

1.1 Study Disease

In 2009 more than 190,000 men were diagnosed with prostate cancer. Despite advances in diagnosis and treatment, in the same year failure rates continue to remain high (27,360 deaths). Local persistence of prostate cancer treated with radiotherapy (RT) is underappreciated. Prostate cancer has a long natural history and the consequences of local persistence may not be realized for over ten years. There is significant evidence in support of doses of 78 Gy or higher for primary treatment of localized prostate.²⁻⁴ There is some evidence to support and we hypothesize that the regions in the prostate with the greatest tumor burden are the regions that are at highest risk of harboring persistent disease after RT. Multiparameter Magnetic Resonance Imaging (MRI), and in particular Dynamic Contrast Enhanced MRI (DCE-MRI) is very promising for the *in vivo* 3D localization of the dominant tumor area.⁵ Delivery of ablative spatially fractionated radiation to the DCE-MRI defined tumor volume may induce significant tumor endothelial cell death and possibly bystander effects including reduced tumor interstitial fluid pressure in densely populated tumors due to rapid cell kill.

Our biomarker studies have revealed that molecular biomarkers found in pretreatment prostate biopsy material are associated with patient outcome. We have published a number of papers on biomarkers, including Ki-67,⁶p53,^{7,8} MDM2,^{9,10} bcl-2 and bax,¹¹ p16,^{12,13}cox-2,¹⁴ and PKA¹⁵ in which abnormal expression using immunohistochemistry (IHC) has been associated with worse patient outcome after radiotherapy. However, no model incorporating such markers has gained acceptance in the clinic. We hypothesize that a significant source of variation in biomarker expression is due to tumor heterogeneity and that it is molecular abnormalities in the dominant tumor areas that are hypervascular on MRI (from angiogenesis) that determine outcome. The proposed studies in this protocol will provide the foundation for biomarker collection in different prostate tumor regions, comparing specifically the functional MRI suspicious and unsuspected regions.

